5.3 Run-in Procedures

There will be no run-in procedures.

5.4 Contraindications

Meriva® may interfere with absorption and efficacy of the chemotherapy drug, irinotecan, captothecin, and cyclophosphamide. However, these individuals would not be eligible for this study.

There is a theoretical pharmcodynamic interaction with turmeric and anticoagulant medications. Therefore, participants on anticoagulant therapy will be excluded. 38-41

Curcumin could theoretically inhibit CYP29C and CYP3A4. Thus, individuals taking medications considered to be sensitive substrates for either of these will be monitored carefully.

5.5 Concomitant Medications

All medications (prescription and over-the-counter), vitamin and mineral supplements, and/or herbs taken by the participant will be documented on the concomitant medication CRF and will include: 1) start and stop date, dose and route of administration, and indication. Medications taken for a procedure (e.g., biopsy) will also be included.

5.6 Dose Modification

In the event of adverse events that are at least possibly related to study agent, and/or at the discretion of the treating physician, a participant may discontinue study agent for a period of one week. If the symptoms have returned to baseline, the participant may be rechallenged at the level of 500 mg once per day for one week, after which the participant can return to the full dose of 500 mg twice per day. If symptoms persist or worsen after the study agent holiday, the participant will be taken off study agent. Please see Sections 8.3 and 8.4 for definitions and details regarding data collection and submission.

If any participant using medications that are substrates of CYP2A9/3A4 develops side effects (Grade 2 or above), we will discontinue study agent for a period of one week. If the symptoms have returned to baseline, the participant may be rechallenged at the level of 500 mg once per day for one week, after which the participant can return to the full dose of 500 mg twice per day. If symptoms persist or worsen after the study agent holiday, the participant will be taken off study agent.

5.7 Adherence/Compliance

5.7.1 Compliance will be defined as a study participant having taken 75% of the required doses. Weekly phone calls will be implemented to increase likelihood that participants comply with study instructions.

5.7.2 Compliance will be determined by participant report (medication diary) and tablet count after review by the site study coordinator. Compliance will be defined as ingestion of \geq 75% of the planned agent doses. The primary endpoint analysis will be based on the intent-to-treat principle, where all randomized patients that complete both the pre-intervention and post-intervention exams will be included. Secondary data analyses will include all randomized participants (i.e. adverse event analyses) or relevant subject subgroups (i.e. those who demonstrate \geq 75% compliance with the study agents), as appropriate.

6. PHARMACEUTICAL INFORMATION

6.1 Study Agent (IND # NCI, Division of Cancer Prevention)

Curcumin derived from the tropical plant *Curcuma longa* has a long history of use as a dietary agent, food preservative, and in traditional Asian medicine. It has been used for centuries to treat biliary disorders, anorexia, cough, diabetic wounds, hepatic disorders, rheumatism, and sinusitis. The preventive and therapeutic properties of curcumin are associated with its antioxidant, anti-inflammatory, and anticancer properties. Extensive research over several decades has attempted to identify the molecular mechanisms of curcumin action. Curcumin modulates numerous molecular targets by altering their gene expression, signaling pathways, or through direct interaction. Curcumin regulates the expression of inflammatory cytokines (e.g., TNF, IL-1), enzymes (e.g., COX-2, LOX, MMP9, MAPK, mTOR, Akt), adhesion molecules (e.g., ELAM-1, ICAM-1, VCAM-1), and apoptosis related proteins (e.g., Bcl-2, caspases, DR, Fas). 32-34 Curcumin modulates the activity of several transcription factors (e.g., NFkB) and their signaling pathways. Based on its ability to affect multiple targets, curcumin has the potential for the prevention and treatment of various conditions, including osteoarthritis.

Meriva® is a botanical extract that contains curcuminoid phytosomes (phosphatidylcholine conjugates). Phytosome technology is a solid state dispersion of botanical into a phospholipid matrix (typically lecithin coming from non GM soy or from sunflower). Hence, it is a form of pre-formulation, designed to boost the bioavailability of botanical compounds. The aspect of this pre-formulation is typically a powder that can then be formulated in topical or oral finished dosage forms (typically tablets, hard and soft gelatin capsules). Lecithin acts as a surfactant at biological level and, contemporarily, decreases the self-aggregation tendency of compounds like polyphenols or triterpenes. The composition of the curcuminoid mixture will include total curcuminoid content of $20\% \pm 2\%$. Of that total percent, the individual composition will be as follows: curcumin (16.3-16.8%), demethoxycurcumin (2.0-2.5%) and bisdemethoxycurcumin (0.25-0.35%).

The formulation of Meriva® that will be used in this clinical trial will be Meriva-500 (as opposed to the sustained release formulation). The overall curcuminoid absorption from the Meriva-500 formulation is about 29-fold higher than that of the corresponding unformulated curcuminoid mixture. The improved absorption and enhanced plasma curcuminoid profile make Meriva an attractive candidate for chemoprevention studies, with an ability to administer doses

significantly lower than unformulated curcuminoid mixtures. Indena S.p.A, will provide the Curcuma phospholipid, Meriva, and is conducting quality control analyses on the raw material as per their standard protocol. Thorne Research will verify identity and conduct microbiological assays prior to production using Thorne Research's in-house Quality Control laboratory. Results of all quality control testing will be reviewed and approved by Thorne Research Quality Control personnel prior to releasing the raw material for manufacture into a finished, encapsulated product.

The placebo used in this study will be manufactured by Thorne Research, Inc. It will be matching in terms of size and color. It will also be matched in terms of excipients such as soy lecithin to improve the likelihood that any effect seen in the active treatment arm is due solely to the curcuminoids.

6.2 Reported Adverse Events and Potential Risks

6.2.1 Adverse events reported to Thorne Research (via SafetyCall) from 6/1/2013 to 12/10/2015:

Total Number of Individuals Submitting Reports	23
Total Number of Symptoms Reported	43
GI-related symptoms	24
Skin, muscle, joint symptoms	9
Miscellaneous	10

Meriva® AE Risk					
Product	Total Number of Individuals Submitting Reports	Reports per Bottle	Reports per Serving		
Meriva-SR (120s)	12	1 in 20,331	1 in 1,219,860		
Meriva 500 (120s)	7	1 in 17,976	1 in 1,078,560		
Meriva 500 (60s)	4	1 in 15,780	1 in 476,393		
Total	23	1 in 18,823	1 in 1,047,040		

6.2.2 Summary of adverse events reported from clinical trials involving Meriva® or curcumin:

In a study of Meriva® for symptomatic primary osteoarthritis (OA), all of the OA symptoms improved in the active group as compared to a placebo group, and there were no reports of liver or kidney toxicity or other adverse events. 42,43 Curcumin-phospholipid formulations studies in central serous chorioretinopathy, chronic anterior uveitis, benign prostatic hyperplasia, and pre-surgical carpal tunnel syndrome noted few, if any, adverse events. The

exact adverse events were not specified.⁴⁴⁻⁴⁷ A report of Meriva for the reduction of serum IL-22 levels in patients with psoriasis vulgaris noted 3 adverse event reports among the individuals on the active treatment arm, including diarrhea and diarrhea with fever, but none were attributed to study intervention.⁴⁸ A study of curcumin for pediatric inflammatory bowel disease noted minimal reports of adverse events, none of which required dose de-escalation and none of which were felt to be related to curcumin.⁴⁹

Regarding utilization of doses higher than in the present study, a dose of 6000 mg curcuminoids/day was well tolerated with the reports of side effects being similar between the active treatment and placebo groups in a study of curcuminoids for the reduction of oral lichen planus. One systematic review of more than 60 completed studies of some form of curcumin, as well as a meta-analysis of randomized controlled trials for a variety of cancer and precancerous conditions, noted few reported adverse events even at doses of up to 8000 mg/day curcuminoids. Star Sharma, et al. reported on a clinical trial in advanced, refractory colorectal cancer involving 0.45 to 3.6 g daily curcumin in which there were 2 reports of diarrhea (Grade 2), one report of nausea (Grade 2), 4 reports of increases in alkaline phosphatase (Grades 1 and 2) and 4 reports of increased lactate dehydrogenase (Grade 1). Dose limiting toxicities were not observed. Dose-escalation studies indicate relative safety of curcumin at doses as high as 12 grams per day for 3 months.

Possible Side Effects of Meriva®*:

Rare, Some May Be Serious

In 100 people receiving Meriva, 3 or fewer may have:

- Loose stool (diarrhea)
- Stomach ache
- Feeling sick to your stomach (nausea)
- Muscle pain (myalgia)
- Joint pain (arthralgia)
- Skin discomfort

6.3 Availability

Meriva® is an investigational agent supplied to investigators by Thorne Research through a collaborative agreement with NCI, Division of Cancer Prevention (DCP) (see Section 12.7).

At baseline and at the 3-month visit, participants will be provided with two bottles, each containing 100 capsules (500 mg per capsule) of Meriva® or matching placebo.

^{*} Meriva® Investigator's Brochure, 12/06/2016

6.4 Agent Distribution

Agent will be shipped from Thorne Research to MRIGlobal for distribution to participating organizations.

Agents will only be released by MRIGlobal after documentation of IRB approval of the DCP-approved protocol and consent is provided to DCP and the collection of all Essential Documents is complete (see DCP website for description of Essential Documents).

NCI, DCP-supplied agents may be requested by the Investigator (or their authorized designees) at each Organization. DCP guidelines require that the agent be shipped directly to the institution or site where the agent will be prepared and administered. DCP does not permit the transfer of agents between institutions (unless prior approval from DCP is obtained). DCP does not automatically ship agents; the site must make a request. Agents are requested by completing the DCP Clinical Drug Request form (NIH-986) (to include complete shipping contact information) and faxing or mailing the form to the DCP agent repository contractor:

[name], MRIGlobal, DCP Chemoprevention Agent Repository [name]

[contact] [contact]

Email: [contact]

Emergency [contact]

6.5 Agent Accountability

The Site Principal Investigator, or a responsible party designated by the Investigator, must maintain a careful record of the inventory and disposition of all agents received from DCP using the NCI Drug Accountability Record Form (DARF). The Investigator is required to maintain adequate records of receipt, dispensing and final disposition of study agent. This responsibility will be delegated to appropriately trained and credentialed study personnel specified on the MAY2015-05-01 Site Delegation of Tasks Logs. Include on receipt record from whom the agent was received and to whom study agent was shipped, date, quantity and batch or lot number. On dispensing record, note quantities and dates study agent was dispensed to and returned by each participant.

Forms required for study agent ordering, accountability, and return are available on the CPN website: http://cancerpreventionnetwork.org

6.6 Packaging and Labeling

Meriva® will be provided to MRIGlobal by Thorne Research, Inc. MRIGlobal is under contract with NCI, Division of Cancer Prevention to serve as the DCP Drug Repository.

Each bottle will be labeled with a one-part label identifying study specific information, including study title, DCP protocol number, investigator name, dosing instructions, number of refills, recommended storage conditions, the name and address of the distributor, Participant ID number, lot number, date of manufacture, final retest date, number of strength of tablets, and a caution statement indicating that the agent is limited to investigational use only and the agent should be kept out of reach of children.

6.7 Storage

In each institutional research pharmacy, capsules must be stored in a locked and secure area at room temperature, $59^{\circ}-86^{\circ}$ F ($15^{\circ}-30^{\circ}$ C) and protect from light and moisture. Participants will be instructed to store their study agent in a location not accessible by children, at room temperature, and protected from light and moisture.

6.8 Pre-Registration and Registration/Randomization

6.8.1 Participant Pre-Registration

6.8.1.1 To pre-register a participant, the participating site will send the completed, signed, and dated Pre-Registration Eligibility Checklist, to the CPN Registration Office (Email: [contact]; [contact]) to pre-register all participants. The CPN Registration Office will enter the information into the CPN-hosted database. A unique participant identification number (PID) will be assigned.

6.8.1.2 At the time of pre-registration, the following will be verified:

- IRB approval at the registering institution
- Participant eligibility (including existence of a signed informed consent document)
- Existence of a signed authorization for use and disclosure of protected health information (USA Institutions only).
- Study agent is available and Drug Shipment Authorization has been granted to the registering site.

The following will also be recorded:

- Participant has/has not given permission to contact them or their physician to learn about the results from this study.
- Participant has/has not given permission for samples and related information to be sent from the Biobank to investigators at other institutions for use in future health research.
- Participant has/has not given permission to have three additional blood draws done along with protocol blood draws and that they may be used for future research to learn about, prevent, treat, or cure cancer and other health problems.
- Participant has/has not given permission to use information from the alcohol and tobacco use questionnaires to be used in future health research.
- Participant has/has not given permission to his/her doctor (or someone from the Cancer

Prevention Network) to contact them in the future to ask them to take part in more research.

- 6.8.1.3 Baseline (screening) evaluations must be completed within the guidelines specified on the Schedule of Events (See Section 7.1).
- 6.8.1.4 Registration Office personnel will automatically register participants separately to the translational components of the study (See Section 13).

6.8.2 Registration

- 6.8.2.1 To register a participant, the participating site will send the completed Registration Eligibility Checklist to the CPN Registration Office (Email: [contact]; [contact]). The CPN Registration Office will enter the information into the CPN-hosted database. For randomization details, see Section 13.2.
- 6.8.2.2 Intervention cannot begin prior to registration and must begin ≤ 14 days from registration.
- 6.8.2.3 Pathology reports confirming diagnoses will be placed in the study participant's file \leq 30 days post Registration/Randomization.
- 6.8.2.4 Once the intervention assignment has been ascertained by the CPN Registration Office, the participant's study medication code numbers will be displayed on the emailed confirmation page. At least two weeks prior to the Month 3 visit, the data manager/nurse/pharmacist at the participant's institution must contact the CPN Registration Office at [contact] for code numbers when additional study product is needed for the participant.
- 6.8.2.5 Stratification Factors collected at baseline (prior to randomization):
 - Enrolling Site: Honduras versus Puerto Rico
 - Gastric mucosal histologic diagnosis: MAG versus GIM versus Both (from screening EGD)

After the participant has been registered on to the study, values of the stratification factors will be recorded. Randomization will be performed by CPN personnel. The CPN electronic-based randomization system will be utilized to ensure that randomization of participants to appropriate study arms while balancing the stratification variables is carried out successfully.

6.9 Blinding and Unblinding Methods

Once the intervention assignment has been ascertained by the CPN Registration Office, the appropriate code numbers for the blinded study agent (Meriva® or placebo) will be communicated to the designated contact (i.e., data manager, study coordinator, nurse, or

MAY2015-05-01 Version 4.0, Amendment 6 May 13, 2019

pharmacist) at the participant's Participating Organization. This ensures that both the participant and the medical professionals who care for the participant are blinded to the intervention assignments.

There are two distinct situations in which it will be deemed appropriate to break the randomization assignment for participants enrolled onto this current trial:

- In the event of an emergency for an individual participant.
- Serious Adverse Event (SAE) that fulfills the criteria for expedited reporting to the FDA.

In these situations, Participating Organization personnel may assume the participant is on active agent and call the CPN Registration Office within one business day to receive unblinding information. The study name/number, participant identifier, participant initials, and bottle number will be required to break the randomization code. The Participating Organizations are responsible for notifying the medical monitor at DCP, NCI of the unblinding event. See Medical Monitor contact information in Section 11.2.

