11.2.2 Reporting SAEs to DCP

11.2.2.1 The Lead Organization and all Participating Organizations will report SAEs on the DCP SAE Report Form found on the CPN website and on the DCP website at this location: http://prevention.cancer.gov/clinical-trials/clinical-trials-management/protocol-information-office/pio-instructions-and-tools/2012-consortia.

11.2.2.2 Contact the DCP Medical Monitor by email (preferred) or phone within 24 hours of knowledge of the event.

[name] [name], FACS
National Institutes of Health, National Cancer Institute, Division of Cancer Prevention
[name]
[name]

[contact]

Fax (with cover sheet, Attn: [name]): [contact]

Email: [contact]

Include the following information when contacting the Medical Monitor:

- Date and time of the SAE
- Date and time of the SAE report
- Name of reporter
- Call back phone number
- Affiliation/Institution conducting the study
- DCP protocol number
- Title of protocol
- Description of the SAE, including attribution to drug

11.2.2.3 The Lead Organization and all Participating Organizations will submit SAE reports within 48 hours of learning of the event via the current, approved SAE reporting process:

The following individuals/entities will be provided with the SAE information within the 48 hour time frame:

- 1. The DCP Medical Monitor at [contact]
- 2. DCP's Regulatory Contractor CCS Associates, Inc. (CCSA; [contact]) at [contact]
- 3. The CPN Operations Office at [contact]
- 11.2.2.4 The DCP Medical Monitor and CCSA regulatory and safety staff will determine which SAEs require FDA submission as IND safety reports.

11.2.2.5 The Lead Organization and all Participating Organizations will comply with applicable regulatory requirements related to reporting SAEs to the CIRB/IEC.

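### Section 6.9 lets site staff obtain the treatment code for an SAE that meets FDA expedited-reporting criteria, although Section 11.2.2.4 gives that reporting decision to the sponsor side and no site need is stated

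*Combined protocol and SAP*

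**What the plan says.** Section 6.9 of the combined protocol and SAP states the purpose of the blind: "This ensures that both the participant and the medical professionals who care for the participant are blinded to the intervention assignments". It then sets out the exceptions: "There are two distinct situations in which it will be deemed appropriate to break the randomization assignment for participants enrolled onto this current trial". The first is an emergency for an individual participant. The second is a "Serious Adverse Event (SAE) that fulfills the criteria for expedited reporting to the FDA".

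The procedure is the same for both: "Participating Organization personnel may assume the participant is on active agent and call the CPN Registration Office within one business day to receive unblinding information". Information about the code break then flows from the site to the sponsor: "The Participating Organizations are responsible for notifying the medical monitor at DCP, NCI of the unblinding event".

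Section 11.2.2.4 places the regulatory decision elsewhere: "The DCP Medical Monitor and CCSA regulatory and safety staff will determine which SAEs require FDA submission as IND safety reports". On timing, Section 11.2.2.2 has the site contact the Medical Monitor within 24 hours of knowing of the event, with a description that includes attribution to drug. Section 11.2.2.3 says that the organizations "will submit SAE reports within 48 hours of learning of the event via the current, approved SAE reporting process".

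Neither section describes a code break limited to the sponsor side, and Section 6.9 gives no reason why the site needs the assignment on the second ground.

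**The concern.** Emergencies have their own ground, so the second ground as written is a regulatory one. The parties that decide whether an SAE goes to the FDA are the Medical Monitor and the regulatory contractor, yet the party that receives the code is the site. The blind can be broken at the site on a criterion that the site does not decide.

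Two kinds of judgment made after the code break are exposed.

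- **Attribution of later adverse events.** Section 7.1 collects adverse events weekly and at Months 3, 6 and 7. Attribution of possible or higher defines toxicity in Section 13.7 and feeds the suspension rule in Section 13.7.1, which is applied to each arm separately.
- **Off-study status.** Section 8.4 allows a participant to go off study by physician decision. Under Section 13.6 only participants with IL-1β at baseline and 6 months are evaluable, and missing values are not imputed. Knowledge of the arm could therefore bear on who reaches the Month 6 biopsy.

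**Working it through.** The plan gives no figure on this point, so the check is a comparison of passages.

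**1. Who decides and who receives the code**

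| Step | Party | Section |
|---|---|---|
| Reports the SAE | Lead and Participating Organizations | 11.2.2.2, 11.2.2.3 |
| Decides on FDA submission | DCP Medical Monitor and regulatory contractor | 11.2.2.4 |
| May request and receive the code | Participating Organization personnel | 6.9 |
| Is told of the code break | DCP medical monitor, by the site | 6.9 |

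The deciding party and the receiving party differ.

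**2. Order of events.** The call in Section 6.9 is timed at one business day, and the SAE report in Section 11.2.2.3 at 48 hours. No section makes the call wait for the decision in Section 11.2.2.4. The site can therefore call before the report is submitted and before the sponsor side has decided, and would then be applying the expedited-reporting test itself. Section 6.9 does not say when the one business day starts, so this order is possible but not certain.

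**3. Force of the wording.** The code break is described as appropriate in the two situations, and personnel may call. It is permitted rather than required. The recipients are site personnel. Investigators are not named, but nothing keeps the code from those who attribute events. Section 11.1.4 does not name the assessor. I take this to be site staff, because Section 11.2.2.2 has the site supply attribution.

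**4. Effect on the suspension rule.** Section 13.7.1 suspends accrual if 2 of the first 10 treated participants, or 20% of all participants once accrual exceeds 10, have had a grade 3 or higher event at least possibly related to treatment. A separate criterion is met by 1 participant with a grade 4 or 5 event at least possibly related to concomitant CYP-sensitive substrates. Both count participants. If the SAE that led to the code break already counts, later events in the same person add nothing under that criterion. A later event matters only if the participant was not already counted.

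**5. How often it could arise.** The documents give no rate of expedited SAEs. For an assumed rate p among the 50 randomized, the expected number is 50p and the chance of at least one is 1 − (1 − p)^50.

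| Assumed p | Expected number | Chance of at least one |
|---|---|---|
| 0.5% | 0.25 | 22% |
| 1% | 0.5 | 39% |
| 3% | 1.5 | 78% |
| 5% | 2.5 | 92% |

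Across this range the provision concerns between none and a few participants. The table shows how often the ground could arise. It does not estimate bias.

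**The case against.** Much of the case on the other side stands.

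- **Automatic unblinding.** A reader might infer that every expedited SAE unblinds the site. The documents do not support this, because the wording permits a request and does not require one. What remains is that the blind is left to site discretion without a clinical reason.
- **The suspension rule.** A reader might infer that each further event attributed with knowledge of the arm brings the trial closer to suspension. It does not if the participant is already counted. Section 13.7.1 also reviews all grade 4 events regardless of attribution, and crossing the rule suspends accrual only temporarily.
- **The index event.** Its attribution is due at the first contact, within 24 hours, so nothing shows that it is made after unblinding. The exposure is to later events.
- **The endpoints.** A reader might infer bias in the primary result. IL-1β is measured by Luminex assay, and Sections 7.4 and 8.3 encourage early discontinuers to complete the remaining evaluations. Off-study status by physician decision remains a route, but a narrow one. The safety endpoint in Section 13.5 compares all adverse events, and Section 13.7 is descriptive and also reviews grade 3 to 5 events judged unrelated or unlikely.
- **Whether the site needs the code.** No section says that expedited reporting can proceed without unblinding the site. The study-specific data and safety monitoring plan and the approved SAE reporting process, neither available here, may cover code handling. The supportable statement is that no need is given and that the decision lies elsewhere.
- **Loss of access.** Section 5.6 has sites stop and rechallenge after possibly related events, so a site may want the code outside an emergency. Section 5.6 does not make those steps depend on the assignment, but restricting access is still a real change for the site.

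**Conclusion.** The point holds as an inconsistency between Sections 6.9 and 11.2.2.4 that weakens, at the margin, the blind that Section 6.9 itself states. Site personnel may obtain the code on a regulatory ground separate from an emergency, possibly before the responsible parties have decided that the ground is met, and with no stated need.

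The size is small. It is confined to later adverse event attribution and off-study decisions in individual participants, and no effect on the primary analysis is shown. It is worth correcting because the correction is cheap, and it is not a reason to doubt the design.

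This rests on three assumptions: site staff make the attributions, no document outside this one already restricts the code, and expedited SAEs are infrequent.

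**What to change.** Reconcile Section 6.9 with Section 11.2.2.4 by stating, for each ground, who receives the code.

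- **Emergency:** leave release to the site as it now stands.
- **Expedited reporting:** have the CPN Registration Office release the code to the DCP Medical Monitor and regulatory contractor only, once they have made the decision in Section 11.2.2.4. State that the site and study team stay blinded unless the emergency ground also applies.
- **Notification:** keep the site's duty to tell the medical monitor for emergency code breaks, and drop it where the monitor is already a recipient of the code.

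The cost is a protocol amendment of a few sentences. The same office holds the codes, and neither the sample size nor the analysis changes. The downside is that a site could no longer obtain the code simply by asking after an expedited SAE that is not an emergency. The sponsor and the sites should confirm that they accept this before the text is changed.
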